#### 6.4.1. Disease Confirmation by Central Pathology Review

As part of the patient's medical history, pathology reports from the time of diagnosis are to be collected. In addition, stained formalin-fixed, paraffin-embedded (FFPE) slides used for PTCL diagnosis must be collected for all patients enrolled and submitted for central pathology review. Refer to lab manual for more details.

### 6.5. Demography

At Screening, patient demographic data will be collected, including date of birth, gender, race, and ethnicity, as allowable according to local law.

# 6.6. Physical Examination

A complete physical examination per standard of care will be conducted at the Screening and EOT visits. Targeted physical examinations should be performed at time points specified in the Schedule of Events (Table 1 and Table 2).

Any physical examination abnormality deemed clinically significant by the Investigator during Screening will be reported as medical history. Any physical examination abnormality that emerges or has worsened after signing of the ICF and that is assessed as clinically significant by the Investigator will be reported as an AE.

## 6.7. Electrocardiogram

A twelve-lead electrocardiogram (ECG) will be conducted during Screening and assessed by the Investigator to confirm eligibility. A single ECG tracing is sufficient unless there is an abnormality, such as prolonged QTcF  $\geq$  480 msec, new arrhythmia, or other clinically significant finding. If an abnormality is observed, the ECG is to be performed in triplicate at least 2 minutes apart. Additional on-treatment or follow-up ECGs should be performed at the Investigator's discretion as clinically indicated.

## 6.8. Echocardiogram

An echocardiogram will be conducted during Screening and assessed by the Investigator to confirm eligibility (patients with baseline LVEF < 50% [or below institution's normal limit] are excluded). Additional on-treatment or follow-up echocardiograms should be performed at the Investigator's discretion as clinically indicated.

# 6.9. Vital Signs, Height and Weight

Vital signs, including temperature (°C), blood pressure, pulse, and respiration rate, as well as weight (kg) will be measured at the time points specified in the Schedule of Events (Table 1 and Table 2). Height (cm) will be measured during Screening only.

Systolic and diastolic blood pressure and pulse will be measured with the patient in a supine or sitting position; the same position will be used for a patient throughout the study. Blood pressure should be assessed on the same arm throughout the study.

# 6.10. Clinical Laboratory Tests

### 6.10.1. Screening Serology

Laboratory studies to assess the status of prior or current CMV infection include CMV serologies, CMV immunoglobulin (Ig) G and IgM, and viral load, are to be conducted during Screening. Patients with a detectable viral load will not be eligible for enrollment. During

duvelisib treatment, periodic CMV viral load monitoring is recommended in patients with a history of CMV reactivation or other opportunistic infections.

Furthermore, a liver serology panel, including HBsAg, HBcAb, and HCV Ab, is to be performed during Screening. Patients with a positive HBsAg or HCV Ab will be excluded. Patients with a positive HBcAb must have negative HBV DNA to be eligible, must receive prophylaxis with entecavir (or equivalent) concomitant with duvelisib treatment, and must be periodically monitored for HBV reactivation by institutional guidelines. Investigators who strongly believe that that a positive HBcAb is false due to passive immunization from previous immunoglobulin infusion therapy should discuss the potential to defer HBV prophylaxis with the Medical Monitor.

HIV and HTLV-1 tests are to be performed during Screening for all patients without documentation of prior negative results.

#### 6.10.2. Pregnancy Test

A serum or urine pregnancy test will be done during Screening and repeated predose on C1D1 for WCBP; results must be available and confirmed to be negative before administration of the first study drug dose. If the Screening pregnancy test is performed within 1 week before C1D1, it need not be repeated on C1D1.

For the Dose Optimization Phase, pregnancy tests are to be repeated during the Treatment Period at the time points designated in the Schedule of Events (Table 1). For the Expansion Phase, pregnancy tests are to be repeated monthly (see Table 2). For cycles where pregnancy testing is the only requirement in the Schedule of Events, the patient may have this done locally. For both phases, the pregnancy test may be repeated as deemed necessary by the Investigator.

#### 6.10.3. Clinical Laboratory Tests

Clinical laboratory tests will be performed by the investigative site's local laboratory. Samples will be collected from patients at scheduled study visits before the administration of study drug unless otherwise noted.

Blood samples for evaluation of the following clinical laboratory tests will be collected at the time points specified in the Schedule of Events (Table 1 and Table 2). Samples may be collected up to 24 hours from the visit. C1D1 laboratory tests do not need to be repeated if performed within 72 hours prior to Screening. All safety Screening/C1D1 laboratory results will be reviewed prior to dosing to ensure patient is eligible.

• **Hematology:** Hemoglobin, hematocrit, platelets, white blood cell count (WBC) with 5-part differential (neutrophils, lymphocytes, monocytes, eosinophils, basophils), such that an absolute neutrophil count and an absolute lymphocyte count (ALC) can be derived, if it is not already provided as part of the laboratory analysis.

- Clinical Chemistries: Sodium, potassium, chloride, bicarbonate, albumin, total protein, creatinine, blood urea nitrogen or urea, lipase, amylase, uric acid, calcium, phosphorus, magnesium, glucose, lactic dehydrogenase, serum ALT, serum AST, total and direct bilirubin, and alkaline phosphatase.
- Serum Quantitative Immunoglobulins (Ig): IgA, IgM, and IgG.
- CD4 Lymphocyte Cell Count (at Screening)

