Survival status													Х

Abbreviations: AE = adverse event; BID = twice daily; CMV = cytomegalovirus; d = day; D = Study Day; ECOG = Eastern Cooperative Oncology Group; EOT = End-of-Treatment; HIV = human immunodeficiency virus; HTLV-1 = human T-lymphotropic virus type 1; M = month; PD = progressive disease; PO = orally; Q2M = every 2 months; SAE = serious adverse event;  $\beta$ -hCG =  $\beta$ -human chorionic gonadotropin.

1. See Section 6 for additional information on each assessment.

- 2. Screening evaluations other than clinical laboratory tests performed within 7 days of C1D1 do not need to be repeated at C1D1 (predose). C1D1 laboratory tests do not need to be repeated if performed within 72 hours prior to Screening.
- 3. All laboratory samples on C1D1 should be collected predose.
- 4. Additional visits may be scheduled / procedures may be performed at the Investigator's discretion, as clinically indicated.

- 5. The End-of-Treatment (EOT) visit is to be performed within 7 days after the last study drug dose. If safety assessments were performed within the previous 2 weeks, they need not be performed at the EOT visit. If disease response assessments were performed within the previous 4 weeks, they need not be performed at the EOT visit.
- 6. Patients who discontinue treatment from duvelisib for reasons other than PD are to have disease response assessments performed Q2M per Table 4 until the development of PD, as determined by the Investigator, death, or initiation of alternate anti-cancer therapy.
- 7. After development of PD, as determined by the Investigator, patients are to be followed Q3M for survival; this follow-up may be conducted via telephone.
- 8. Stained Formalin-fixed, paraffin-embedded (FFPE) slides used for PTCL diagnosis must be collected for all patients enrolled and submitted for central pathology review. See lab manual for details.
- 9. Additional on-treatment or follow-up electrocardiograms should be performed at the Investigator's discretion as clinically indicated.
- 10. Additional on-treatment or follow-up echocardiograms should be performed at the Investigator's discretion as clinically indicated.
- 11. Vital signs, including temperature, blood pressure, pulse, and respiration rate, and weight (kg) are to be measured. Height (cm) to be measured only at Screening.

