# 4. STUDY DESIGN

# 4.1. Overview of Study Design

This is a multi-center, parallel cohort, open-label, Phase 2 study of duvelisib, an oral dual inhibitor of PI3K- $\delta$ , $\gamma$ , in patients with relapsed/refractory PTCL. The study has 2 phases, a Dose Optimization Phase and an Expansion Phase.

Regardless of study phase, all patients will undergo screening assessments up to 30 days before the first study drug dose (Cycle 1, Day 1 [C1D1]). Patients meeting all of the entrance criteria, based on Screening assessments, will be enrolled in the study and receive the first study drug dose on C1D1. Thereafter, patients will attend study center visits as per the applicable Phase Schedule of Events (Dose Optimization: Table 1, Expansion Phase: Table 2). At screening, disease will be measured using F-fluorodeoxyglucose-positron emission tomography (FDG-PET)-computed tomography (CT) scanning (PET-CT) (CT images along with PET should be diagnostic with contrast unless contraindicated). Where PET-CT is not feasible, CT with contrast or magnetic resonance imaging (MRI) may be used after discussion with the Medical Monitor. Subsequently, for FDG-avid PTCL, PET-CT will be used to assess disease status and for FDG-non-avid PTCL, CT with contrast or MRI will be appropriate substitutes. The modality chosen to evaluate response in each individual patient should be the same throughout the duration of the study. For the purposes of patient management during the conduct of the study, the Investigator's assessment of disease response will be used. Images also will be centrally stored, and disease response will be determined by an IRC for futility and at the end of the study.

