## 6.3. Inclusion and Exclusion Criteria

All patients must meet the inclusion and exclusion criteria prior to being enrolled in the study. Eligibility criteria will be reviewed during Screening and again prior to dosing on C1D1.

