4.7 Baseline Values

Unless otherwise specified, the baseline value is defined as the most recent value prior to first study drug administration.

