5.3.2 Laboratory Data

Laboratory tests will be reported separately for hematology, blood chemistry and serum quantitative immunoglobulins (Ig).

For the purposes of presentation in both tables and listings, the following laboratory test results will be converted to the International System of Units (SI) before presentation: sodium, potassium, chloride, bicarbonate (or CO₂), albumin, total protein, creatinine, uric acid, calcium, phosphorus, magnesium, glucose, total and direct bilirubin, alkaline phosphatase, red blood cell (RBC) count, hemoglobin, hematocrit, platelets, white blood cell count (WBC) with 5-part differential performed manually or by flow cytometry (lymphocytes, neutrophils, monocytes, basophils, and eosinophils), amylase, lipase, alanine aminotransferase (ALT), aspartate aminotransferase (AST), IgA, IgM and IgG. Laboratory tests will be graded according to CTCAE Version 5.0.

If a laboratory test value is reported using a non-numeric qualifier (e.g., less than [<] a certain value or greater than [>] a certain value), the given numeric value will be used in the summary statistics, ignoring the non-numeric qualifier.

For continuous laboratory results, descriptive statistics will be provided by visit for observed value and change from baseline. Plots of mean observed value over time will be produced for continuous laboratory test results.

For laboratory tests graded by CTCAE, the following summary tables will be created by treatment arm:

- Summary of worst post-baseline value on treatment, regardless of baseline value according to the following categories:
 - Any grade
 - Grade 1-2
 - Grade 3-4
 - Grade 3
 - o Grade 4
- Summary of worst post-baseline value on treatment that represents a worsening in grade from baseline (shift table) according to the following categories:
 - Any grade
 - Grade 1-2
 - Grade 3-4
 - o Grade 3
 - o Grade 4

In addition, laboratory tests with Grade 3 or 4 laboratory values will be presented in a separate patient listing.

Laboratory tests with bi-directional grades (e.g., hyperglycemia and hypoglycemia) will be presented separately for each direction within each by grade summary table.

For laboratory tests not graded by CTCAE, the following summary tables will be created by treatment arm:

- Summary of worst post-baseline value on treatment, regardless of baseline value according to the following categories:
 - Low (less than lower limit of normal)

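### The C1D1 laboratory waiver counts 72 hours back from Screening, not from C1D1, so a first dose may rest on laboratory results about 30 days old

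*Protocol*

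**What the plan says.** Protocol Section 6.10.3 states: "C1D1 laboratory tests do not need to be repeated if performed within 72 hours prior to Screening". Footnote 2 of Table 1 (Dose Optimization Phase) and footnote 2 of Table 2 (Expansion Phase) carry the same sentence.

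On the timing of Screening, Section 4.1 says that "all patients will undergo screening assessments up to 30 days before the first study drug dose", and both schedules show it as Day -30 to Day -1. Both schedules also mark hematology and chemistry at Screening, at C1D1 and next at C1D8.

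Two other waivers stand close by:

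- Footnote 2 opens with the rule for non-laboratory evaluations: "Screening evaluations other than clinical laboratory tests performed within 7 days of C1D1 do not need to be repeated at C1D1 (predose)".
- Section 6.10.2 covers the pregnancy test: "If the Screening pregnancy test is performed within 1 week before C1D1, it need not be repeated on C1D1".

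Two rules call for a check before dosing. Section 6.10.3 says "All safety Screening/C1D1 laboratory results will be reviewed prior to dosing to ensure patient is eligible", and Section 6.3 says "Eligibility criteria will be reviewed during Screening and again prior to dosing on C1D1".

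For analysis, SAP Section 4.7 says that, unless otherwise specified, "the baseline value is defined as the most recent value prior to first study drug administration". SAP Section 5.3.2 uses that baseline for change from baseline and for the table described as "Summary of worst post-baseline value on treatment that represents a worsening in grade from baseline (shift table)".

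**The concern.** A waiver of a predose blood draw makes sense only if a recent result already exists. Here recency is measured from Screening, which can itself lie 30 days before the first dose. The interval that matters, from last sample to first dose, is left open.

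The stake is mainly safety. Eligibility depends on hemoglobin, platelets, creatinine, bilirubin and AST/ALT (inclusion criterion 6), and the limits are permissive. The platelet floor of 25 × 10⁹/L sits at the level below which Table 8 withholds drug, so a small fall between Screening and C1D1 matters. Expansion Phase patients start at 75 mg BID, which Section 1.3 identifies as the maximum tolerated dose. Section 1.2 reports transaminase elevation of Grade 3 or higher in 11 of 35 patients (31%) with T-cell lymphoma in the earlier phase 1 experience.

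There is a smaller consequence for analysis. An old Screening value would serve as the laboratory baseline, so change since the sample but before treatment would appear as change on treatment.

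**Working it through.** The plan gives no figure to reproduce. The check is a comparison of texts followed by date arithmetic.

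**1. Anchors side by side**

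| Waiver at C1D1 | Look-back | Counted from | Source |
|---|---|---|---|
| Non-laboratory evaluations | 7 days | C1D1 | Tables 1 and 2, footnote 2 |
| Pregnancy test | 1 week | C1D1 | Section 6.10.2 |
| Clinical laboratory tests | 72 hours | Screening | Section 6.10.3; Tables 1 and 2, footnote 2 |

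Footnote 2 takes laboratory tests out of the 7-day allowance, which suggests a tighter limit was intended for them. The sentence that follows gives them a looser one.

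**2. Age of the newest predose result when the waiver is used**

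Inputs: Screening on Day -30 to Day -1 (Section 4.1, Tables 1 and 2); look-back 72 h = 3 days.

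- Scheduled Screening sample drawn, C1D1 draw waived: age = days from Screening to C1D1 = 1 to 30 days.
- Pre-Screening sample also replaces the Screening draw: maximum age = 30 + 3 = 33 days.
- Same 72 hours counted from C1D1: maximum age = 3 days.

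**3. Gap to the next scheduled draw**

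Hematology and chemistry are next due at C1D8 ± 3 days, and Day 8 is 7 days after Day 1.

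- From a Day -30 Screening sample: 30 + 7 = 37 days.
- With the late end of the visit window: 37 + 3 = 40 days.

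**4. Whether another rule closes the gap**

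- Footnote 3 says samples taken on C1D1 are to be predose. It governs draws that take place and does not restore one that was waived.
- The eligibility re-check in Section 6.3 and the results review in Section 6.10.3 can both be met by re-reading the Screening report. Neither sets a maximum age.
- Section 9.1 requires eligibility to be met and documented before dosing, again without an age limit.
- The 24-hour tolerance in Section 6.10.3 concerns samples collected for a visit, not a waived draw.

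**5. The opposite failure**

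Read literally, the sentence gives no waiver for a panel drawn at a Screening visit 48 hours before dosing. That is the case a sensible waiver would cover.

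**The case against.** The strongest reply is that the waiver will seldom apply. It requires a sample taken in the 72 hours before Screening. A patient whose first laboratory tests are the scheduled Screening ones does not qualify, and the C1D1 draw still stands. Consent must precede Screening procedures (inclusion criterion 12), and Section 6.2 exempts only standard-of-care procedures. A sample taken before consent would thus have to be routine care, and to replace the whole C1D1 draw it would need lipase, amylase, uric acid and IgA/IgM/IgG as well as the usual counts and chemistry. This stands. It limits how often the problem can occur, but laboratory work is local and a routine panel shortly before Screening is plausible.

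A second reply is that this is an obvious slip, because a C1D1 test cannot come before Screening, and that the surrounding text points to fresh samples. It probably is a slip. All three places agree, however, so a site that looks elsewhere for clarification finds the same wording.

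Third, CD4 count, CMV viral load and echocardiography are scheduled only at Screening, so the design already accepts values up to 30 days old. That is true of those tests. Hematology and chemistry are different: the schedule separately requires them at C1D1.

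Finally, a correction now reaches few patients. Figure 1's note says the Dose Optimization Phase is complete, so the Table 1 edit is for consistency only. SAP Section 3.5 counts 101 Expansion patients enrolled before protocol version 7.0. With a ceiling of 130, at most 130 − 101 = 29 could come after that. This limits the benefit of the correction but does not make the rule right.

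**Conclusion.** The concern holds: the waiver is wrong as written and should be corrected. When it is used, the newest predose results may be up to 30 days old (33 at the extreme), against 3 days with the evident intended anchor. The gap to the next scheduled draw can reach 37 days, or 40 with the visit window.

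These are worst cases. They assume a qualifying pre-Screening sample, Screening at Day -30, a site that applies the sentence literally, and no extra draw at the investigator's discretion. The documents give no frequency for any of these.

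The consequence is a weakened safety check at first dose and, for the patients concerned, an older baseline in descriptive laboratory tables. The primary ORR analysis, the power statement, the classification of treatment-emergent adverse events and the worst-grade table made regardless of baseline do not change. That places the point at should-fix rather than must-fix.

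**What to change.** In Section 6.10.3 and in footnote 2 of Tables 1 and 2, change the anchor so that C1D1 laboratory tests may be omitted only if performed *within 72 hours prior to the first dose on C1D1*. Footnote 3, Section 6.3 and the SAP can stay as they are, because the baseline rule in SAP Section 4.7 then picks up a value at most 3 days old when the waiver is used.

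The cost is one phrase in three places and at most a few extra routine blood draws. The change also allows a Screening panel taken within 72 hours of dosing to stand in for the C1D1 draw, so some patients may be spared one.

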#### 6.11. Disease and Response Assessment

At Screening, disease will be measured using PET-CT (CT images with PET should be diagnostic with contrast unless contraindicated). Where PET-CT is not feasible, CT with contrast or magnetic resonance imaging (MRI) may be used after discussion with the Medical Monitor. Subsequently, for FDG-avid PTCL, PET-CT will be used to assess disease status and for FDG-non-avid PTCL, CT with contrast or MRI will be appropriate substitutes. In all cases, disease status will be assessed using the Lugano criteria (Cheson et al, 2014). The modality chosen to evaluate each individual patient should be the same throughout the duration of the study, if feasible. Response and progression will be assessed as indicated in Table 7.

PET images are to be assessed using the 5-point scale (5PS), a semi-quantitative analysis that is a pragmatic yet robust predictor of patient outcome (Table 6).

Score	Criterion
1	No uptake above background
2	Uptake ≤ mediastinum
3	Uptake > mediastinum, but $\leq$ liver
4	Uptake moderately > liver*
5	Uptake markedly higher than liver and/or new lesions*
Х	(New) areas of uptake unlikely to be related to lymphoma

Table 6:5-Point Scale (Lugano Classification)

\*It is suggested according to published data that score 4 be applied to uptake greater than the maximum standardized uptake value (SUV) in a large region of normal liver and score 5 to uptake 2× to 3× greater than the maximum SUV in the liver. Source: Barrington et al. Role of imaging in the staging and response assessment of lymphoma: consensus of the International Conference on Malignant Lymphomas Imaging Working Group Clin Oncol. 2014 Sep 20; 32(27): 3048–3058.

At each scheduled disease response assessment (Table 3 or Table 4), a PET-CT- or CT-based response will be determined, based on the Lugano response criteria for patients with malignant lymphoma (Table 7).

 Table 7:
 Response Criteria for Malignant Lymphoma

Response and Site	PET-CT-based Response	CT-Based Response
Complete Response	Complete metabolic response	Complete radiologic response (requires all of the following)

Response and Site	PET-CT-based Response	CT-Based Response
Lymph nodes and extralymphatic sites	Score of 1, 2, or $3^*$ with or without a residual mass on 5PS† It is recognized that in Waldeyer's ring or extranodal sites with high physiologic uptake or with activation within spleen or marrow (e.g., with chemotherapy or myeloid colony-stimulating factors), uptake may be greater than normal mediastinum and/or liver. In this circumstance, complete metabolic response may be inferred if uptake at sites of initial involvement is no greater than surrounding normal tissue even if the tissue has high physiologic uptake	
Non-measured lesions	Not applicable	Absent
Organ enlargement	Not applicable	Regress to normal
New lesions	None	None
Bone marrow	No evidence of FDG-avid disease in bone marrow	Normal by morphology; if indeterminate, IHC negative
Partial Response	Partial metabolic response	Partial remission (all of the following)
Lymph nodes and extralymphatic sites	5PS score 4 or 5 with reduced uptake compared with baseline and residual mass(es) of any size During treatment, these findings suggest responding disease At end of treatment, these findings indicate residual disease	$\geq$ 50% decrease in SPD of up to 6 target measurable nodes and extranodal sites When a lesion is too small to measure on CT, assign 5 mm × 5 mm as the default value When no longer visible, 0 × 0 mm For a node > 5 mm × 5 mm, but smaller than normal, use actual measurement for calculation
Nonmeasured lesions	Not applicable Absent/normal, regressed increase	
Organ enlargement	Not applicable	Spleen must have regressed by $\geq 50\%$ in length beyond normal
New lesions	None	None
Bone marrow	Residual uptake higher than uptake in normal marrow but reduced compared with baseline (diffuse uptake compatible with reactive changes from chemotherapy allowed). If there are persistent focal changes in the marrow in the context of a nodal response, consideration should be given to	Not applicable

Response and Site	PET-CT-based Response	CT-Based Response
	further evaluation with MRI or biopsy or an interval scan	
Stable disease (no response)	No metabolic response	Stable disease
Target nodes/nodal masses, extranodal lesions	5PS score 4 or 5 with no significant change in FDG uptake from baseline at interim or end of treatment	< 50% decrease from baseline in SPD of up to 6 dominant, measurable nodes and extranodal sites; no criteria for progressive disease are met
Non-measured lesions	Not applicable	No increase consistent with progression
Organ enlargement	Not applicable	No increase consistent with progression
New lesions	None	None
Bone marrow	No change from baseline	Not applicable
Progressive Disease	Progressive metabolic disease	Progressive disease requires at least 1 of the following:
Individual target nodes/nodal masses	5PS score 4 or 5 with an increase in intensity of uptake from baseline and/or	PPD progression
Extranodal lesions	New FDG-avid foci consistent with lymphoma at interim or end-of- treatment assessment	An individual node/lesion must be abnormal with:
		LDi > 1.5 cm and
		Increase by $\geq$ 50% from PPD nadir and
		An increase in LDi or SDi from nadir
		$0.5 \text{ cm for lesions} \le 2 \text{ cm}$
		1.0  cm for lesions > 2  cm
		In the setting of splenomegaly, the splenic length must increase by > 50% of the extent of its prior increase beyond baseline (e.g., a 15-cm spleen must increase to > 16 cm). If no prior splenomegaly, must increase by at least 2 cm from baseline New or recurrent splenomegaly
Non-measured lesions	None	New or clear progression of
		preexisting nonmeasured lesions
New lesions	New FDG-avid foci consistent with lymphoma rather than another	Regrowth of previously resolved lesions
	inflammation). If uncertain	A new node $> 1.5$ cm in any axis
	regarding etiology of new lesions, biopsy or interval scan may be considered	A new extranodal site $> 1.0$ cm in any axis; if $< 1.0$ cm in any axis, its presence must be unequivocal and must be attributable to lymphoma

Response and Site	PET-CT-based Response	CT-Based Response	
		Assessable disease of any size unequivocally attributable to lymphoma	
Bone marrow	New or recurrent FDG-avid foci	New or recurrent involvement	

Abbreviations: 5PS=5-point scale; CT=computed tomography; FDG=fluorodeoxyglucose; IHC=immunohistochemistry; LDi=longest transverse diameter of a lesion; MRI=magnetic resonance imaging; PET=positron emission tomography; PPD=cross product of the LDi and perpendicular diameter; SDi=shortest axis perpendicular to the LDi; SPD=sum of the product of the perpendicular diameters for multiple lesions.

\*A score of 3 in many patients indicates a good prognosis with standard treatment, especially if at the time of an interim scan. However, in studies involving PET where de-escalation is investigated, it may be preferable to consider a score of 3 as inadequate response (to avoid undertreatment). Measured dominant lesions: Up to 6 of the largest dominant nodes, nodal masses, and extranodal lesions selected to be clearly measurable in 2 diameters. Nodes should preferably be from disparate regions of the body and should include, where applicable, mediastinal and retroperitoneal areas. Non-nodal lesions include those in solid organs (e.g., liver, spleen, kidneys, lungs), gastrointestinal (GI) involvement, cutaneous lesions, or those noted on palpation. Nonmeasured lesions: Any disease not selected as measured, dominant disease and truly assessable disease should be considered not measured. These sites include any nodes, nodal masses, and extranodal sites not selected as dominant or measurable or that do not meet the requirements for measurability but are still considered abnormal, as well as truly assessable disease, which is any site of suspected disease that would be difficult to follow quantitatively with measurement, including pleural effusions, ascites, bone lesions, leptomeningeal disease, abdominal masses, and other lesions that cannot be confirmed and followed by imaging. In Waldeyer's ring or in extranodal sites (e.g., GI tract, liver, bone marrow), FDG uptake may be greater than in the mediastinum with complete metabolic response but should be no higher than surrounding normal physiologic uptake (e.g., with marrow activation as a result of chemotherapy or myeloid growth factors).

Source: Cheson, BD, et al. Recommendations for initial evaluation, staging, and response assessment of Hodgkin and non-Hodgkin lymphoma: the Lugano classification. J Clin Oncol 2014;32(27):3059-3067.

